7.2 General Methodology

7.2.1 Reports for which this Statistical Analysis Plan Applies

This SAP applies to the trial report for Pre-market Approval Application (PMA) to the Food and Drug Administration (FDA) and the final report.

This SAP applies to the trial report for CE mark submission and to the report for regulatory submissions in other geographies.

The analyses for CE mark approval and FDA approval may be used for regulatory submissions in other geographies.

This SAP applies to the main trial manuscript, though the manuscript may not include all analyses specified in this document.

7.2.2 Special Considerations

7.2.2.1 Report Timing and Cutoff Dates

Cutoff dates will be applied to all site case report forms. A Visit Cutoff Date and a Received Cutoff Date will be used. The visit cutoff date will be the first date on which at least 800 patient-years of data have been collected for the PMA report. The visit, assessment, and event dates will be used to determine which case report forms satisfy the visit cutoff date. The received cutoff date will be determined near the time of the database closure and will be chosen to ensure that all forms of critical importance have been received while still allowing adequate time for data cleaning between the received cutoff date and the date of database closure. The "logints" log-in timestamp field will be used to determine which case report forms satisfy the received cutoff date. CE mark report Visit Cutoff Date and a Received Cutoff Date will be used similarly when regulatory submission data requirement is met.

Any forms which do not have a visit date directly on the form will use the visit date from the corresponding form for that entry. Forms with multiple dates will apply cutoff dates to individual lines of data on the form.

7.2.2.2 Definition of Enrolled Subject

An enrolled subject is defined as a subject whose IRB/MEC-approved patient informed consent form has been signed and dated by all required parties.

7.2.2.3 P-Values

The statistical test for the safety objective will be performed at one-sided α =0.05. All reported p-values greater than or equal to 0.0001 will be rounded to four decimal places. P-values less than 0.0001 will be displayed as "<0.0001."

7.2.2.4 Kaplan-Meier Analyses

Kaplan-Meier analysis of event-free rates (or event rates) will be performed at 30 days, 6 months, 12 months and annually through five years. These times correspond to 30 days, 180 days, 365 days, 730 days, 1095 days, 1460 days, and 1825 days, respectively. At each time point with data, the product-limit estimate of the event-free rate (or event rate), the number of subjects at risk, the number of

Revision 7.0

Page 11 of 22

subjects with events, the number of subjects censored, and the loglog transformed 95% confidence interval using the Greenwood standard error will be presented.

For subjects without an event, the date of censoring will be the latest date of all follow-up visits, assessments, and events (including death).

7.2.2.5 17 mm and 29 mm Valves

If at the time of PMA and CE mark submissions, PERIGON Pivotal trial does not have fifteen 17mm subjects successfully implanted with Model 400 valve and followed for at least one year, 17mm study data from PERIGON Japan Trial will be utilized to support 17mm market approval in United States and other global geographies.

The PERIGON Japan Trial with 17mm valve is a prospective, interventional, non- randomized, multisite trial to evaluate the safety and effectiveness of the 17mm aortic bioprosthesis in a patient population undergoing surgical aortic valve replacement with the similar inclusion and exclusion criteria as the PERIGON Pivotal trial.

Similarly for 29 mm valve, if at the time of PMA and CE mark submission, PERIGON Pivotal trial does not have fifteen 29 mm subjects successfully implanted with Model 400 valve and followed for at least one year, the enrollment may continue for 29 mm subjects until the regulatory requirement is met.

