7.1.1.3 Sample Size

Sample size estimation is based on the methods of Grunkemeier²⁴. The amount of data required to test the null hypothesis using the smallest acceptable adverse event rate of 1.2% per patient-year (excluding Valve Thrombosis, Major Hemorrhage and Major PVL) is 800 patient-years. This estimation assumes a 95% confidence level, a power of 0.80, and an annual attrition rate of 5%. If all subjects are enrolled within a one year time frame, and followed for one year postoperatively, then a total of 556 implants are required. Accounting for potential variability in attrition and enrollment rate, a sample size of 650 was originally approved in protocol revisions 1B through 1D. With version 1E of the investigational protocol, the sample size has been increased to 1300. While the increased sample size adds exposure of the investigational device to a larger cohort of patients, the sample size is within acceptable limits based on the following justification:

- The current risk and benefit analysis suggests that the benefits of surgical aortic valve replacement far outweigh the risks associated with implant of an aortic bioprosthesis. Given the relatively low expected incidence of late valve-related adverse events and the assumed linearized occurrence of such events as detailed in the published OPC data from the FDA Heart Valve Guidance 2010 and ISO5840:2009, the increased risk to the overall population of subjects requiring SAVR is minimal.
- Due to the linearized OPC model utilized in the evaluation of the primary safety endpoints, an increased sample size will allow for a more rapid evaluation of the primary safety endpoints through faster accumulation of valve-years.
- A similar sample size has been used by both Medtronic and other industry sponsors in the evaluation of other tissue aortic valves that have a similar design, the same intended use, and the same primary safety endpoints as the PERIGON trial. Notably, the pivotal trial for the Medtronic Mosaic™ valve utilized a cohort of 1252 subjects for evaluation of the primary safety endpoints which were compared to the same published OPC. Likewise, the most recently approved tissue aortic valve, Trifecta™, which is manufactured by St. Jude Medical, utilized a cohort of 1014 subjects for evaluation of the primary safety endpoints compared to the same published OPC. Therefore, there is historical precedent that a cohort similar to that of the PERIGON trial is justified.

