7.4 Handling of Missing, Unused, and Spurious Data and Dropouts

Every effort will be undertaken to minimize missing data. In time-to-event outcomes, dropouts will be censored at the time of discontinuation, consistent with the Kaplan-Meier approach. Unless specified otherwise in each objective, no statistical techniques will be used to impute missing data. If a subject's data are missing for any reason, that subject will not be included in that portion of the analysis. The number of subjects included in each analysis will be reported so that the potential impact of missing data can be assessed.

In the case of partial dates, the general rule is as follows:

- If only the month and year are known, the event or assessment will be analyzed as if it occurred on the 15th of that month.
- If only the year is known, the event or assessment will be analyzed as if it occurred on June 30th of that year.

These resolutions of partial dates are subject to the restrictions that pre-procedure events and assessments must occur between the enrollment date and the procedure date, and post-procedure events and assessments must occur no earlier than the procedure date. If additional information about the partial dates might be known, for example, the event occurs after 15th of the month, then data may be analyzed as if it occurred on the 16th of the month.

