7.9.1.3 Data Collection and Analysis Methods

7.9.1.3.1 Data Collection and Analysis

Adverse device effects and outcomes will be identified and reported by the Investigator at all visits. All deaths and endpoint related adverse events will be reviewed by the CEC.

Early postoperative events are defined as those occurring on or before 30 days post-operative. Late postoperative events are those occurring after 30 days post-operative.

Early rates of adverse events will be calculated as the number of early adverse events divided by the total number of subjects, expressed as a percentage.

The late events rates will be calculated using the linearized event rate methodology. That is, the rate will be the number of late events divided by the late post-operative patient-years. For those adverse events with OPC available, the linearized rates and their associated one-sided upper 95% confidence bounds will be compared to the Objective Performance Criteria (OPC) to show that they are within acceptable limits. Formally, the method introduced by Cox^{iv} which gives the relatively most accurate results^v will be used:

χ .95,2 n_e +1/2Y_T

where ne is the number of late events and YT is the late post-operative patient-years. If there is 0 events, the one-sided upper 95% confidence bound will be 0.

Kaplan-Meier survival analyses will also be performed to summarize valve-related adverse events and death. The Kaplan-Meier rate and the corresponding 95% confidence interval will be presented for each visit interval. In addition, number of subjects at risk, number of events, number of censored subjects and the Kaplan-Meier survival curve or event curve will also be displayed.

In addition, control articles based on current literature of previously approved heart valves will be selected. Adverse event data from the control articles will be provided so as to inform the reader of the current state of heart valve technology, as expressed by articles in quality peer-reviewed journals, and allow additional evaluation of the Model 400 adverse event data.

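### Kaplan-Meier summaries of non-fatal valve events censor at death, so 1-KM read as an event rate overstates the share of patients affected; add cumulative incidence beside it

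*SAP*

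**What the plan says.** SAP 7.2.2.4 sets the estimator and the horizon: "Kaplan-Meier analysis of event-free rates (or event rates) will be performed at 30 days, 6 months, 12 months and annually through five years". The same section gives the censoring rule for subjects without an event: "the date of censoring will be the latest date of all follow-up visits, assessments, and events (including death"). SAP 7.4 treats withdrawals in the same way: "dropouts will be censored at the time of discontinuation, consistent with the Kaplan-Meier approach".

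SAP 7.9.1.3.1 says where this applies: "Kaplan-Meier survival analyses will also be performed to summarize valve-related adverse events and death". Protocol 7.1.1.4 plans Kaplan-Meier summaries of the adverse events too, and Protocol 7.2.1.5 and SAP 7.8.1.4 do so for the interim report.

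The formal safety comparison uses a different measure. In SAP 7.9.1.3.1, for late events, "the rate will be the number of late events divided by the late post-operative patient-years", and the upper confidence bound of that rate is set against the OPC limit.

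Neither document plans a cumulative incidence function or mentions competing risks.

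**The concern.** Both documents define the safety endpoint through how often valve events and deaths occur over time (Protocol 7.1.1.1, SAP 7.9.1.1). Thromboembolism, endocarditis, structural valve deterioration (SVD), reintervention and explant cannot happen after death. If deaths are censored, 1-KM estimates the risk in a hypothetical population in which nobody dies. That differs from the share of implanted patients who have the event, yet SAP 7.2.2.4 allows the output to be called an event rate without any qualification.

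Explant raises a related question. Under Protocol 4.4.4 and Table 2, an explanted subject is followed for safety for 30 days and then leaves the trial. Such a subject becomes an ordinary censored observation although the study valve is gone.

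What is at stake is how the long-term percentages are read. The SAP governs the regulatory reports, the final report and the main manuscript (SAP 7.2.1). There is no upper age limit and follow-up runs to five years, so deaths will occur. Readers may take the 5-year figures as a patient's own risk.

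**Working it through.** The documents state no Kaplan-Meier figure, so there is nothing of the plan's own to reproduce first.

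**Inputs**
- Event hazards h from the OPC table (Protocol Table 8): thromboembolism 2.5, endocarditis 1.2 and valve thrombosis 0.2, in % per patient-year.
- Horizon: 5 years (Protocol 2.2).
- Death hazard m: **not given for this trial**. Assumed 2, 4 and 6% per year. The documents offer two loose reference points. For attrition, Protocol 7.1.1.3 says: "This estimation assumes a 95% confidence level, a power of 0.80, and an annual attrition rate of 5" per cent, with deaths not separated from other losses. Protocol 1.1 cites 22% survival at 18 years with another pericardial valve, which is -ln(0.22)/18 = 8.4% per year if constant.

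**Formulas, constant hazards**
- 1-KM(t) = 1 - exp(-h·t)
- Cumulative incidence with death competing: CIF(t) = h/(h+m) × [1 - exp(-(h+m)·t)]

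**Worked case.** Thromboembolism, m = 4%, t = 5:
- 1-KM = 1 - exp(-0.125) = 11.75%
- CIF = (0.025/0.065) × [1 - exp(-0.325)] = 0.3846 × 0.2775 = 10.67%
- Gap 1.08 points; 11.75/10.67 = 1.10, so 10% in relative terms.

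**Five-year results**

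| Event hazard | 1-KM | CIF at m = 2 / 4 / 6% | Gap, points | Relative excess |
|---|---|---|---|---|
| 2.5%/PY | 11.75% | 11.19 / 10.67 / 10.18% | 0.56 / 1.08 / 1.57 | 5 / 10 / 15% |
| 1.2%/PY | 5.82% | 5.54 / 5.28 / 5.04% | 0.28 / 0.54 / 0.78 | 5 / 10 / 16% |
| 0.2%/PY | 1.00% | 0.95 / 0.90 / 0.86% | 0.05 / 0.09 / 0.14 | 5 / 10 / 16% |

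At the two reference rates, 2.5%/PY gives a CIF of 10.42% (m = 5%, excess 13%) and 9.63% (m = 8.4%, excess 22%, 2.1 points).

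**Earlier time points.** For 2.5%/PY and m = 4%, the figures are 2.47% against 2.42% at 1 year and 4.88% against 4.69% at 2 years.

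**Late-rising hazard.** For illustration only, take a Weibull hazard of shape 3 with a 5-year 1-KM of 3.0%, so H(t) = -ln(0.97)·(t/5)³. Neither the shape nor the 3.0% comes from the documents. Integrating H′(t)·exp(-H(t) - m·t) from 0 to 5 gives 2.78, 2.58 and 2.40% for m = 2, 4 and 6%. The relative excess is about 8, 16 and 25%. The gaps are 0.22, 0.42 and 0.60 points, smaller than those for thromboembolism at the same mortality.

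**Effect on the formal tests.** With constant hazards, expected events are h·A and expected patient-years are A, where A = [1 - exp(-(h+m)·t)]/(h+m). Their ratio is h whatever m is. A simulation of 2,000,000 subjects with m = 5% agreed: linearized rates of 1.21% and 2.50% for true hazards of 1.2% and 2.5%, while 5.2% and 10.4% of subjects actually had the event by 5 years. The interim Z statistic (SAP 7.8.1.4) is also late events over late patient-years, and the sample size (SAP 6.1) is a Poisson calculation in events and patient-years. None of them uses Kaplan-Meier.

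**The case against.** The strongest reply is that this is no error. Freedom from event with deaths censored is an accepted device-focused summary of how the valve performs while patients are alive, and SAP 7.2.2.4 never claims to estimate the share of patients affected before death. That stands. The weakness is in calling 1-KM an event rate with no patient-level figure beside it, and a label alone would remove much of it.

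The size can also be challenged. It rests on assumed mortality. With all 1300 subjects and no censoring, the 95% half-width 1.96·√[p(1-p)/1300] is about 1.75 points at 11.75% and 1.3 points at 5.82%, so the gaps at 4% mortality lie within sampling error. That stands as a statement of scale, although a difference between two target quantities does not shrink as data accumulate. Early reports are barely affected. The PMA data cut falls at 800 patient-years (SAP 7.2.2.1), which over the 556 implants of the sample size section averages 800/556 = 1.4 years each.

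A reader might infer that the safety conclusion itself is compromised. The documents do not support that: the hypothesis tests use linearized rates. Nor is a risk being hidden, because 1-KM errs towards more events.

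Finally, the SAP introduction expects analyses beyond the plan, so nothing bars the addition. That makes it easy, but does not specify it in advance.

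**Conclusion.** The point holds as a low-cost reporting improvement. Censoring at death makes 1-KM exceed the proportion of implanted patients who have a non-fatal valve event. The direction is certain wherever deaths occur among patients still at risk.

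The size is conditional. For constant hazards and an assumed 2 to 6% annual mortality, the 5-year excess is about 5 to 16% in relative terms, at most about 1.6 points for the event rates tabulated, and negligible at 1 year. A late-rising hazard such as SVD may show a larger relative excess, but it would be wrong to infer that the largest absolute distortion falls there: in the illustration the gap in points is smaller than for thromboembolism.

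The effect is conservative for the device and limited to descriptive summaries. It does not reach the OPC tests, the interim Z test or the sample size, and it does not apply to all-cause death.

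**What to change.** In SAP 7.2.2.4 and 7.9.1.3.1:

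- For each non-fatal event, add the Aalen-Johansen cumulative incidence with death as a competing event, at the time points already planned, and label it as patient-level risk.
- Keep the Kaplan-Meier figure beside it for comparison with the control articles, labelled as freedom from event with deaths censored.
- Treat explant as a competing event only for events other than explant and reintervention. Protocol 4.4.4 counts removal or replacement of the valve as a reintervention, so letting explant compete there would discard true events.
- Count an event that leads to explant, or that falls on the same date, as the event and not as the competitor.
- Keep Kaplan-Meier alone for all-cause death.

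No new data are needed: deaths are reviewed by the Clinical Events Committee and explants are recorded on the reintervention form. The cost is one more column per table, the tie rule above, and a one-line note explaining why each event has two figures.

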7.2.2.6 Data Safety Monitoring Board (DSMB)

A DSMB will be established to review accumulating data from the trial, advise Medtronic on the continuing safety of current and future trial participants, and the continuing validity and scientific merit of the trial.

Additional details about the DSMB are outlined in the DSMB charter.

7.3 Center Pooling

Geographies will be United States, Canada and European. Sites that successfully implanted less than 5 subjects will be considered "small sites" and will be pooled together as one site.

The evaluation of the effect of sites and geographies over time to valve-related adverse events and death will be performed as follows:

Cox Proportional Hazards model will be used to evaluate the site and geographies effect on valverelated adverse events. If the resulting p-value for site is > 0.15, the data will be considered to be poolable across trial sites and geographies. Otherwise, if the resulting p-value for site is ≤ 0.15 , further exploratory analysis will attempt to identify covariates that may explain possible heterogeneity among the sites and geographies. All other possible clinically meaningful baseline risk factors then will also be included in the above model as independent variables. A backwards elimination process will be utilized to pare the model down. In this process, the single-term baseline variable with the highest p-value will be removed from the model (except sites and geographies) until all factors have a p-value less than 0.15.

The possible clinically meaningful baseline risk factors include age at implant, gender, preoperative NYHA classification, previous aortic valve replacement, valve size, and concomitant CABG.

Medtronic PERIGON Pivotal Trial Sta	tistical Analysis	Form
Revision 7.0	Page 12 of 22	Medtronic

If this multivariate model does result in p-value of site > 0.15 after adjustment for these baseline factors, then outcome results will again be considered poolable across trial sites. If the resulting p-value for site is still \leq 0.15 after adjustment for these factors, results will be presented by investigational center and the clinical significance of these differences will be assessed.

Any observation with missing values for the response or explanatory variables will be excluded from the analysis.

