1.2 Purpose

The purpose of this pivotal trial is to evaluate the safety and effectiveness of the Medtronic Model 400 aortic valve bioprosthesis [herein referred to as Model 400 valve] in a patient population undergoing SAVR. The collected data will be used to support regulatory applications in seeking market approval for the valve in Europe (CE Mark), the United States, Canada and other geographies. The Model 400 valve is commercially available (Avalus™) in the valve sizes: 19mm, 21mm, 23mm, 25mm, and 27mm after receiving FDA approval on July 31, 2017, Health Canada Approval on September 8, 2017, and CE mark approval on July 3, 2017. The size 17mm and 29mm valve sizes are still considered investigational in all geographies.

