7.3.3 Poolability of Data

A poolability analysis among geographies, investigational sites and baseline data will be performed for the safety endpoint and will be described in detail in the SAP. In addition, the endpoints will be evaluated for possible differences between genders.

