7.9.3.1 Safety Endpoints

The safety endpoints include the valve-related adverse events of Thromboembolism, PVL, reoperation, explant and all-cause mortality. Events that occurred in less than five subjects will not be evaluated by the additional analyses.

The additional safety endpoint analyses described in Section 7.9.3.1 will be included in regulatory submissions to all geographies except for Risk Factor Analysis which will be included only in the submission in US.

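### SAP 7.3 declares data poolable across geographies from the site p-value alone; the fitted geography effect enters no decision and no planned output

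*SAP*

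**What the plan says.** Protocol 7.3.3 makes the commitment and leaves the detail to the SAP: "A poolability analysis among geographies, investigational sites and baseline data will be performed for the safety endpoint".

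SAP 7.3 names three geographies (US, Canada, Europe), merges sites with fewer than 5 implants into one, and fits a Cox model for the effects of site and geography on valve-related adverse events. The rule is then: "If the resulting p-value for site is > 0.15, the data will be considered to be poolable across trial sites and geographies". At or below 0.15, baseline covariates are added and pared down; the one with the highest p-value "will be removed from the model (except sites and geographies) until all factors have a p-value less than 0.15". If the adjusted site p-value exceeds 0.15, "then outcome results will again be considered poolable across trial sites". If not, "results will be presented by investigational center and the clinical significance of these differences will be assessed".

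Of the further safety analyses the SAP says "The additional safety endpoint analyses described in Section 7.9.3.1 will be included in regulatory submissions to all geographies", with the risk factor analysis reserved for the US. They cover valve size, gender and risk factors. None is by geography, and geography is not among the listed risk factors.

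On scope, SAP 7.2.1 states: "This SAP applies to the trial report for Pre-market Approval Application (PMA) to the Food and Drug Administration (FDA) and the final report". It also covers the CE mark report, submissions elsewhere and the main manuscript.

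**The concern.** The trial is single-arm and pools three regions, so a statement that the regions can be pooled supports the pooled event rates. As written, a report can make that statement although the regional difference was either not tested or was tested only as a small part of a broad site comparison. It need not show regional rates either. If the adjusted step is reached, the question of geography is left undecided, because that step concludes on sites only.

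**Working it through.** The documents give no operating characteristics for the pooling rule, so there is no stated figure to reproduce. The check has two parts: the text of the rule, then an illustration of its behaviour.

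**1. The branches of SAP 7.3**

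| Criterion | Conclusion or action | Geography result used? |
|---|---|---|
| Site p > 0.15 | Poolable across sites and geographies | No |
| Site p ≤ 0.15 | Covariate search | No |
| Adjusted site p > 0.15 | Poolable across sites | No; geographies not named |
| Adjusted site p ≤ 0.15 | Results by center | No |

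**2. What the site p-value can show.** Apart from the merged small-site group, each site lies in one region. With 40 sites, the 39 degrees of freedom (df) between sites split into 2 between regions and 37 between sites within regions.
- Site given geography uses only the 37 within-region df and does not respond to a regional difference.
- Site alone spreads the 2-df regional contrast over 39 df.
- Fixed site terms absorb the geography contrast, so the two sets of fixed effects are aliased. The SAP does not say which site test is meant.

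**3. Event counts.** With 1300 subjects, 5 years of follow-up (Protocol 2.2) and 5% annual attrition (Protocol 7.1.1.3), the upper limit is 1300 × (1 − 0.95^5)/(−ln 0.95) = 1300 × 4.41 ≈ 5,733 patient-years. At OPC rates this gives 5,733 × 1.2% = 69 events (endocarditis, all paravalvular leak) to 5,733 × 2.5% = 143 (thromboembolism). I use 70 and 140. The pre-market approval (PMA) cutoff of 800 patient-years gives 800 × 1.2% = 9.6 to 800 × 2.5% = 20.

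**4. Illustration.** There are 22 US, 14 European and 4 Canadian sites. The patient shares of 45/45/10% are assumed; they respect the US cap of 650 out of 1300. Site sizes are assumed unequal and at least 5, with constant Poisson rates. Site and plain geography tests are calibrated to 15% false flags when neither sites nor regions differ. The European rate is assumed to be twofold. CV is the coefficient of variation of the true rate between sites within a region.

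| Share declared poolable | 70 events | 140 events |
|---|---|---|
| CV 0: site alone | 69% | 39% |
| CV 0: site given geography | about 85% | about 85% |
| CV 0: plain geography test | 13% | 1% |
| CV 0.5: site alone | 21% | 3% |
| CV 0.5: site given geography | 36% | 10% |
| CV 0.5: plain geography test | 19% | 6% |
| CV 0.5: geography test allowing for site variation | 29% | 16% |

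A separate calculation with equal site exposure, 4,000 patient-years, a rate of 2.5% and no site variation agrees for CV 0. At a European ratio of 2, site alone declares 36% poolable, site given geography 86%, and a geography test 100 − 98.5 = 1.5%.

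**5. The test that allows for site variation.** A dispersion-scaled F test served as a simple stand-in for a random site effect. At CV 0.5:
- Power for twofold Europe is 0.714 and 0.845 at 70 and 140 events, hence the 29% and 16% in the table.
- Power for threefold Europe is 0.396 at 10 events and 0.631 at 20, so about 60% and 37% are missed.
- With no regional difference it flags 19% and 20% at 70 and 140 events, against 31% and 42% for the plain test.

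Across five independent event types at 0.15, the chance of at least one false flag is 1 − 0.85^5 = 56%.

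**The case against.** The strongest reply is that little depends on this rule. Poolability gates no hypothesis test. The wording about the site p-value may be loose drafting, since the model is said to evaluate both effects. SAP section 3 expects analyses beyond the plan, and results by center would let a reader see the region. If sites really differ, the rule seldom declares poolability: at CV 0.5 and 140 events, site alone does so in 3% of trials, fewer than the 16% for the geography test that allows for site variation. The counts also treat each event type singly. If non-overlapping types were combined, the OPC rates sum to 2.5 + 0.2 + 1.4 + 1.2 + 1.2 = 6.5%, or 52 events at 800 patient-years, and the SAP does not say which applies.

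Most of this stands as a limit on size. It does not supply the missing rule. The flags at CV 0.5 come partly (site alone) or wholly (site given geography) from differences between sites, so they do not answer the geography question. Results by center appear only after the site test has failed twice. Analyses that are merely permitted do not meet the commitment in Protocol 7.3.3. If the wording is loose, correcting it is simple.

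**Conclusion.** The point holds as a defect in a stated rule. SAP 7.3 draws a conclusion about geographies from a p-value for sites, and nothing elsewhere in the SAP provides the geography analysis that the protocol promises. This reading of the text needs no assumption.

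The size is uncertain. The rate ratios, patient shares, site sizes and CV are assumptions, and no document supports a particular regional ratio. The gap is large without site variation within regions and small or reversed at CV 0.5.

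A reader might infer more than the documents support:
- **That the regions differ, or that the pooled safety result is unsound.** The documents give no regional rates, and the comparison with twice the OPC does not depend on the pooling rule.
- **That the rule hides a regional difference about 85% of the time.** That figure belongs to site given geography with no site variation within regions.
- **That past approvals are affected.** The 10- and 20-event cases correspond to the PMA cutoff, and Protocol 1.2 reports approval of the 19 to 27 mm sizes in 2017. What remains is the final report and manuscript.
- **That the 17 and 29 mm sizes are affected.** Protocol 1.2 says "The size 17mm and 29mm valve sizes are still considered investigational in all geographies". But SAP 7.2.2.5 works with fifteen subjects per size and may draw 17 mm data from a trial in Japan, outside the three geographies. No claim is made about size-specific analyses.

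The impact is therefore limited to the poolability statement and the regional presentation.

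**What to change.** Amend SAP 7.3 as follows:
1. Limit the conclusion of the site rule to pooling across sites.
2. Base any statement about pooling across geographies on a separate 2-df geography test at the SAP's own 0.15 level. Fit it without fixed site terms, and allow for site clustering by a random site effect or site-clustered variance.
3. If that p-value is at or below 0.15, run the covariate step already described and present results by geography.
4. Whatever the p-value, report late linearized rates with confidence intervals for the US, Canada and Europe. These are needed because the test has limited power at low counts, and an assumed 10% Canadian share gives only about 7 of 70 events.

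The cost is SAP wording, one more model per event type and one table, on data the trial already collects. The downside is about 15% false flags per event type, about 20% if sites vary with CV 0.5, and about 56% for at least one flag across five independent types. Each flag leads to the planned covariate step and one extra table. The form of the clustering adjustment is open: neither a random-effect nor a clustered-variance model was itself simulated, and with only 4 Canadian sites a clustered 2-df test may be unstable.
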